3.2.2 Analysis population

The analysis populations will be precisely defined and validated during the data review meeting.

Consort Flow Chart

3.2.2.1 mITT population

All selected patients who have confirmed their signed informed consent and for whom:

- the EPIONE device has been set up for the procedure,
- the assistance with the EPIONE device for needle insertion was confirmed before starting the planning phase.

3.2.2.2 PP Population

All patients for whom the planning with the EPIONE device has been initiated according to the protocol without any major deviations.

3.2.2.3 Safety Population

All patients who have confirmed their signed informed consent.

[figure not shown]

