Study flowchart / Organigramme de l'étude	
The diagram illustrates the study timeline. It starts with a 'Pre-intervention consultation' leading to 'Visit 0' (V0=D0). This is followed by an 'Inclusion visit' and the 'Day of the intervention'. After 'Visit 0', the timeline continues to 'Visit 1' (D0+3w ≤ V1 ≤ D0+8w), which includes a 'Follow-up visit' and a 'Post-intervention visit'.

	
The interventional radiologist will explain to the patient the planned procedure(s) and will present the response plan and its different steps during a pre-intervention consultation. The investigator:
 
 - will present the study and the device to the patient (oral and written information), - will review the inclusion and non-inclusion criteria of the study, and assess the patient's eligibility for the study, - Will provide the information letter and informed consent form to the patient, who must be able to read them and have time to think about his or her potential participation in the study prior to consent. - 
Demographics/medical data prior the intervention will be collected the day of the intervention if the patient returns a signed consent form and the investigator confirms the eligibility criteria. No data will be collected while prior intervention consultation, before signature of the written consentment.

Sample size / Taille de l'échantillon	
The size of the sample of at least 67 insertions was calculated to assess the non-inferiority of the successful insertion rate of the introducer (with the help of EPIONE), using a reference proportion of 96% and with a non-inferiority threshold of 0.08 under the assumption of 97% of feasibility for the study.
 
In line with centers practice, that is to say an average of 2 insertions per patient (different locations of possible musculoskeletal disorders, different possible treatments during the same procedure), it is planned to include a minimum of 34 patients in this study.

Randomisation and blinding / Randomisation et aveugle	
Not applicable.

Investigation Number: EPIBONE

ClinicalTrials.gov ID:

CIV-ID: 2024-A00468-39

Document title: EPIBONE Clinical Investigation Synopsis

Doc No: CA-BO-SYN-0053

Revision: B

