3.2 Population

The study population consists of individuals who benefited from the assistance of the EPIONE robot during CT-guided percutaneous bone procedures, namely patients with musculoskeletal disorders.

¹ <https://ansm.sante.fr/uploads/2022/02/04/20220204-modalites-pratiques.pdf>

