3.3 Visits

The study is composed of the following visits:

- Visit 0: Inclusion visit (day of the intervention),
- Visit 1: Follow-up visit (visit post-intervention).

The study flow chart is detailed in Appendix 1 (see section 9.1).

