6.1.2 Secondary analyses

6.1.2.1 Secondary endpoint n°1

The objective of this analysis is to evaluate the safety of the EPIONE robotic assistance for bone percutaneous procedures.

The number of adverse events (AEs) will be described overall, by intensity, severity, and relationship with the device on a descriptive table. The frequency and percentage of AEs, ADEs, SAEs, SADEs, minor and major complications along with the 95% confidence interval, will be presented.

This analysis will be conducted on the safety population.

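### The safety population requires only signed consent, so any consented patient never exposed to EPIONE dilutes the per-patient ADE and SADE rates or their upper limits

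*SAP*

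**What the plan says.** SAP 3.2.2.3 gives the whole definition of the safety population as "All patients who have confirmed their signed informed consent". SAP 6.1.2.1 sets out the safety reporting: "The frequency and percentage of AEs, ADEs, SAEs, SADEs, minor and major complications along with the 95% confidence interval, will be presented". It then states: "This analysis will be conducted on the safety population". The text available describes no second safety set and no analysis limited to exposed patients.

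The mITT definition in SAP 3.2.2.1 also starts from consent but adds two conditions. The first is that "the EPIONE device has been set up for the procedure". The second is that use of robotic assistance had been confirmed ahead of planning.

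Two other statements bear on the point. SAP 3.2 says: "The study population consists of individuals who benefited from the assistance of the EPIONE robot during CT-guided percutaneous bone procedures". SAP 3.2.2 says: "The analysis populations will be precisely defined and validated during the data review meeting". The protocol synopsis (Statistical methods) assigns the safety analysis to a security population that it does not define.

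**The concern.** Consent and exposure are different events, and the SAP's own mITT rule treats them so: its added conditions matter only if some consented patients can fail them. Those patients leave mITT but stay in the safety set.

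For a listing of every AE, a consent-based set is coherent. For device-related rates it is the wrong denominator. A patient in whom EPIONE was never set up or used cannot contribute an ADE or SADE to the numerator, yet adds one to a per-patient denominator, so the bias can go only one way. For all-cause AEs the direction is not fixed, because unexposed patients can have AEs of their own; those rates would simply mix assisted and unassisted experience.

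Safety is the first secondary objective of a study that SAP section 3 calls pivotal and that is meant to support a new indication. A reader will take the ADE and SADE percentages and their upper limits as describing patients treated with the device. If anyone is unexposed, they would not.

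**Working it through.** **Where 34 comes from.** The documents give no ADE or SADE rate to reproduce. The only denominator available is the planned minimum of 34 patients in SAP 3.2.1, and it does follow from the plan's inputs (97% expected, bound 0.88, one-sided alpha 5%, power 90%, arcsine method):

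- h = 2·asin(√0.97) − 2·asin(√0.88) = 0.3593
- n = ((1.645 + 1.282)/0.3593)² = 66.33, rounded up to 67 insertions
- 67/2 = 33.5, rounded up to 34 patients

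**Inputs for the check.**

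- Safety N = 34 (SAP 3.2.1).
- Two-sided 95% intervals for analyses other than the primary (SAP 5.2). The interval method is not named; Clopper-Pearson is assumed.
- k = number of consented patients never exposed. The documents do not give it, so it is an assumption, shown as a range. Every mITT patient had the device set up, so k cannot exceed safety N minus mITT N.
- Percentages are taken as per patient, with ADEs possible only in the 34 − k exposed patients.

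**Formulas.** With x patients having an ADE, the SAP reports x/34, while the rate in exposed patients is x/(34 − k). The reported rate is therefore the exposed rate multiplied by (34 − k)/34, a relative understatement of k/34. With x = 0 both rates are zero and only the upper limit moves: it is 1 − 0.025^(1/n), which gives 10.28% for n = 34 and 12.34% for n = 28.

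**Results.** The k = 0 row is what would be reported on all 34; the other rows are what applies to exposed patients.

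| k unexposed | Exposed n | No ADE: upper limit | One patient with an ADE: rate (upper limit) | Relative understatement of a non-zero rate |
|---|---|---|---|---|
| 0 | 34 | 10.28% | 2.94% (15.33%) | 0 |
| 1 | 33 | 10.58% | 3.03% (15.76%) | 2.9% |
| 2 | 32 | 10.89% | 3.13% (16.22%) | 5.9% |
| 4 | 30 | 11.57% | 3.33% (17.22%) | 11.8% |
| 6 | 28 | 12.34% | 3.57% (18.35%) | 17.6% |

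**If unexposed patients are replaced.** The figure of 34 is a minimum. If recruitment continued until 34 patients were exposed, the safety N would be 34 + k. With k = 4 and no ADE, the reported limit would be 1 − 0.025^(1/38) = 9.25%, against 10.28% in the 34 exposed. The direction is the same and the size similar.

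**The case against.** The strongest reply is that the text shows a gap in wording, not an understated rate. Four points support it.

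- **There may be no unexposed patients.** SAP 3.3 places inclusion on the day of the intervention, and the synopsis (Study flowchart) says: "Demographics/medical data prior the intervention will be collected the day of the intervention if the patient returns a signed consent form". That leaves little time for a patient to drop out between inclusion and set-up. This stands as a limit on size. It does not remove the gap, since same-day inclusion does not guarantee set-up and mITT tests for set-up separately.
- **The unit is not stated.** The definition of the endpoint in SAP 2.2.1 and the opening of 6.1.2.1 both count events. If the percentages are shares of events, the dilution does not arise. A 95% confidence interval fits a per-patient or per-procedure proportion better, but the ambiguity is real and the unit has to be stated.
- **The definition may change, or be supplemented elsewhere.** The data review meeting is to finalise the populations, and Section 9.4 and the figure after 3.2.2.3 are not in the text available, so an exposed-only table cannot be excluded. Neither supplies a different rule in writing. A denominator for device-related events is better fixed in the SAP than at a meeting held with the data in view.
- **The shifts are small, and a reader might rebuild the rate.** The flow chart and individual listings might allow it. The first part is right; the second asks the reader to correct the main safety table.

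It is also fair that an exposure rule based on set-up keeps patients in whom the robot was set up but never guided an instrument. Some dilution could therefore remain, which is why the criterion has to be spelled out.

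**Conclusion.** The concern holds. Followed as written, SAP 3.2.2.3 and 6.1.2.1 put every consented patient in the denominator of device-related rates, and any unexposed patient lowers the per-patient ADE or SADE rate, or its upper limit when there are no events. The direction is certain under per-patient reporting; the size depends on a number the documents do not give. It is nil if everyone is exposed, and for one or two unexposed patients of 34 it is 0.3 to 0.6 percentage points on the zero-event upper limit (10.58 − 10.28 and 10.89 − 10.28). Even at six unexposed the shift, about 2.1 points (12.34 − 10.28), is small beside an interval that already reaches above 10%. The safety analysis is descriptive, so no test, threshold or primary conclusion changes. The point is worth correcting because it concerns who the safety figures describe, and because the remedy is cheap. The conclusion rests on per-patient percentages, the Clopper-Pearson method, and no exposed-only analysis in the parts of the SAP not available.

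**What to change.** Before database lock:

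1. Keep the consent-based set for listing all AEs.
2. State in 3.2.2.3 and 6.1.2.1 that ADE and SADE rates with their 95% intervals, and any all-cause rate meant to describe EPIONE-assisted procedures, are per patient. Their denominator should be the consented patients in whom EPIONE was set up or used, whatever the outcome of the insertion.
3. Say what counts as set up, using the same criterion as mITT.
4. Report the number of consented but unexposed patients and list their AEs separately.
5. Align the definition with SAP 3.2 and with the security population named in the synopsis. If the full clinical investigation plan, not available here, defines that population, the two must agree.

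The cost is SAP wording and one extra table or listing. Set-up status must already be known for each patient in order to apply mITT, so no new data item should be needed. Device-related rates or upper limits become slightly less favourable if anyone turns out to be unexposed; otherwise no result changes.

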3.3 Visits

The study is composed of the following visits:

- Visit 0: Inclusion visit (day of the intervention),
- Visit 1: Follow-up visit (visit post-intervention).

The study flow chart is detailed in Appendix 1 (see section 9.1).

3.3.1 Study outline

4 - Subject Evaluations

4.1 Demography

The following demographic data were collected:

- Age
- Sex
- Weight (Kg)
- Height (Kg)

4.2 Patient History

Relevant data relating to the patient's history were collected:

- Oncology
- "High-energy" traumatic fractures
- "Low-energy" traumatic fractures

4.3 Concomitant treatment (V0)

Relevant data relating to the patient's concomitant treatment at baseline were collected.

4.4 Type of MSK disorders

- Bone tumors: benign or malignant / bone metastases
- Weakened / fractured bone
- Type of medical procedure(s) performed

4.5 End of Study, Premature Termination, and Withdrawal/Discontinuation from the Study

4.5.1 End of Study

A patient will have definitively completed the study when he or she has completed all study visits, with the end-of-study visit corresponding to visit 1.

4.5.2 Early termination

A patient will have stopped the study early in the event:

- decided by the patient
- decided by the sponsor:

The date and reason for this early termination of study participation will be entered on the appropriate page of the case report form (CRF). Patients are withdrawn from the study the date of this decision.
- decided by the investigator:
 - o Patient health or safety event that, on the investigator's advice to not allow the patient to participate to study visits,
 - o Failure to comply with the clinical investigation procedure,
 - o Pregnancy,
 - o In the event of an ADE, judged by the investigator to be severe and which could jeopardize the health of the patients, the investigator may stop the study in agreement with the sponsor.
- decided by the competent authority:
 - o Inability of the investigator(s) to enroll patients according to the planned schedule
 - o Lack of signed consent
 - o Major violations of the protocol/ lack of investigating center compliance
 - o Incomplete or erroneous data
 - o Safety concern
- due to patient lost to follow-up:
 - o A patient will be considered lost to FU if a member of the research team has not heard from the patient after 3 attempts to contact him/her.

4.5.3 Withdrawal/Discontinuation from the Study

Patients are always free to withdraw from the study without giving any justification. When a patient withdraws consent, he/she will be asked for the possibility of using the data already collected. If he/she objects to this, the data will be archived and will be excluded from the study analysis. No further justification will be requested.

5 - Statistical considerations

5.1 Descriptive statistics

Each collected parameter will be described for the entire study population.

- **Qualitative variables** will be described using the count and percentage of each variable, as well as the number of missing data points. Patients with missing data will not be included in the percentage calculations. The handling of missing data will depend on the variable being analyzed (see Section 5.5.2).

- **Quantitative variables** will be described by the number of observed values, mean, standard deviation, median, extreme values (minimum and maximum), and the number of missing data points. Data management (missing, outlier, incomplete data) will be handled based on the variable being analyzed (see Section 5.5).

5.2 Statistical tests

All tests other than the non-inferiority test of the primary endpoint will be two-sided with a global alpha risk level of 5%. A p-value less than 0.05 will be considered statistically significant. All confidence intervals will be two-sided and presented with a 95% confidence level.

The non-inferiority test of the primary criterion will be one-sided with a global alpha risk level of 5%. A p-value less than 0.05 will be considered statistically significant. Confidence interval will be one-sided and presented with a 95% confidence level.

5.3 Duration

The duration (in days) will be calculated as the difference between the start date and the end date + 1. (For example, the duration of a medication (in days) = end date of the medication - start date of the medication + 1).

5.4 Data management

5.4.1 Treatment of missing data

No methodology for dealing with missing data has been implemented in this study.

Any subject with missing data for the primary endpoint will be considered censored for the primary analysis. The same process will be applied to the secondary endpoints.

If there is a significant number of missing values for a subject (or if data has been confirmed as being incorrect), a decision will be made in consultation with the Sponsor regarding the handling of this data.

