2.1.1 Definition of the primary endpoint

The primary endpoint is the successful introducer insertion with the assistance of the EPIONE device. Any insertion of an introducer with the EPIONE device is considered successful if it has not been converted to manual insertion.

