3.2.1 Sample size

The sample size calculation was performed based on a one-sample non-inferiority test design. The preclinical study showed that 96% of insertions assisted with the EPIONE device were successful. Assuming 97% feasibility with EPIONE system, with a clinically acceptable margin of 0.08, the sample size necessary to achieve 90% power and maintain the type I error rate at 5% for this non-inferiority margin was calculated to be approximately 67 insertions.

[figure not shown]
The sample size was calculated using the Cohen's arcsine transformation, which is a preferred method when dealing with proportions close to the boundaries (0 or 1) as it helps to stabilize the variance and normalize the data.

Considering the practice of the centers, i.e. an average of 2 introducer insertions per patient (different locations of MSK disorders possible, different treatments possible during the same procedure), it is planned to include a minimum of 34 patients in the study.

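### SAP 5.4.1 censors whole subjects for a binary endpoint counted per insertion, and the supplied text plans no sensitivity analysis for unknown primary outcomes (minor)

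*SAP*

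**What the plan says.** SAP 5.4.1 opens with "No methodology for dealing with missing data has been implemented in this study" and then gives a rule: "Any subject with missing data for the primary endpoint will be considered censored for the primary analysis". Its next sentence extends the rule to the secondary endpoints. The section closes by leaving a significant number of missing values for a subject, or data confirmed as incorrect, to a decision taken with the sponsor. No threshold or timing is given.

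SAP 5.1, on descriptive statistics, says "Patients with missing data will not be included in the percentage calculations". It also says "The handling of missing data will depend on the variable being analyzed (see Section 5.5.2", and for quantitative variables it points to Section 5.5. Section 5 ends at 5.4.3, so neither target exists.

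The unit of the endpoint is the insertion. SAP 2.1.1: "Any insertion of an introducer with the EPIONE device is considered successful if it has not been converted to manual insertion". SAP 3.2.1 sizes the study at about 67 insertions, assuming "an average of 2 introducer insertions per patient". SAP 6.1.1 tests the proportion of successful insertions in the mITT population against 0.88. It gives one analysis and names no confidence-interval method. The only alternative analysis in the supplied text is in SAP 5.4.2 and concerns outliers in the deviations.

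**The concern.** Censoring belongs to time-to-event data. Here each insertion is either converted to manual or not, and the SAP does not say what a censored insertion contributes to numerator or denominator.

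The unit is a second problem. For a patient with one known and one unknown insertion, the literal rule (and SAP 5.1, which also speaks of patients) removes both. A known success or a known conversion is then lost. A looser reading removes only the unknown insertion. Two analysts could obtain different denominators, and sometimes different conclusions, from the same data.

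Third, either reading is complete-case. If unknown outcomes are more often failures, the observed rate is too high, and nothing planned in the supplied text would show it. One route is an mITT patient whose assistance was confirmed but for whom no insertion is recorded. SAP 3.2.2.1 admits such a patient, and the plan does not say whether this is a failure, a missing value or not counted.

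**Working it through.** **Inputs.** Limit 0.88 = 0.96 − 0.08 (SAP 6.1.1); assumed true rate 0.97, 90% power, arcsine method (SAP 3.2.1); one-sided 5% (SAP 5.2); 34 patients × 2 = 68 insertions. Missing rates, and independence of insertions within a patient, are assumptions.

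**The plan's own figure.** h = 2·asin(√0.97) − 2·asin(√0.88) = 0.3593. n = ((1.645 + 1.282)/h)² = 66.33, rounded up to 67. The SAP's figure reproduces.

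**Pass rule.** The Clopper-Pearson lower bound for x successes in n is the 5% quantile of Beta(x, n − x + 1). At n = 66, 67 and 68 it reaches 0.88 with at most 3 failures. At n = 67 the exact type I error is 0.033 and power 0.858.

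**Does the unit matter?** 67 insertions: 62 successes, 4 failures, 1 missing, with the missing insertion and one failure in the same patient.

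| Handling | x/n | Clopper-Pearson | Wilson | Wald |
|---|---|---|---|---|
| Drop the subject | 62/65 | 0.885 pass | 0.890 pass | 0.911 pass |
| Drop the insertion | 62/66 | 0.867 fail | 0.872 fail | 0.891 pass |
| Missing as failure | 62/67 | 0.850 fail | 0.855 fail | 0.873 fail |

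**Do unknown outcomes matter?** 67 insertions, 2 failures, 2 missing. Excluded: 63/65, Clopper-Pearson 0.906, pass. Missing as failure: 63/67, 0.869, fail. Wilson agrees (0.911, 0.874); under Wald both pass (0.934, 0.893). For m = 0, 1, 2, 3 missing of 67, the most observed failures that still pass under Clopper-Pearson is 3 throughout when missing are excluded, and 3, 2, 1, 0 when they count as failures. At m = 4, missing-as-failure cannot pass.

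**Illustration of lost data.** Let c(n) be the largest number of failures that passes. Under subject exclusion with random missing rate m, the pass probability is Σₖ Bin(k; 34, (1 − m)²) · P(Bin(2k, 0.03) ≤ c(2k)). Clopper-Pearson at a true 0.97: complete data 0.853; m = 1%, 0.855; m = 5%, 0.780. Dropping only the insertion at m = 5% gives 0.850. Most of the fall is a discreteness step: c is 3 at n = 63 (power 0.879) and 2 at n = 62 (power 0.715).

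**Direction.** At a true 0.88 with 5% random missingness, the false-pass rates for subject exclusion against insertion-level exclusion are Clopper-Pearson 2.7% and 3.7%, arcsine 6.2% and 7.1%, Wilson 4.3% and 4.1%, Wald 10.7% and 10.0%. No direction is consistent.

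**Failure-linked missingness**, Clopper-Pearson, true 0.88. Complete data 3.0%; 5% of failures missing, about 4%; 20% of failures missing, about 9 to 10% under either reading. Counting missing as failure restores 3.0%.

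**The case against.** The outcome is observed in the room on the day of the intervention, and a conversion is a recorded failure, not a missing value. Missing outcomes may be rare. The 9 to 10% false-pass figure needs one failure in five to go unrecorded, which nothing in the documents suggests; at one in twenty the rate stays below 5%. Sections 2.1.1, 3.2.1 and 6.1.1 all count insertions, and SAP 5.1 suggests that censored means left out, so a careful analyst could recover a workable rule. All of this stands. It limits the consequence but does not supply the rule.

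Three stronger readings are tempting and should not be made.

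- *That losing one patient leaves the trial short.* The 68 planned insertions are only one above 67. But the pass rule is the same at n = 66, 67 and 68, with Clopper-Pearson power 0.864, 0.858 and 0.853. Both figures are also minimums: "it is planned to include a minimum of 34 patients in the study" and, in the protocol synopsis, "The size of the sample of at least 67 insertions was calculated".
- *That the subject rule favours the device.* At a true 0.97 with 5% random missingness, the insertion-level analysis passes and the subject-level one fails in 7.9% of simulated trials under Clopper-Pearson. The reverse change, towards the device, stayed below 2% in the scenarios run.
- *That no sensitivity analysis exists anywhere.* Only the protocol synopsis is supplied. The full clinical investigation plan and the table list in SAP Section 9.4 are not, so the statement is limited to the supplied text.

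**Conclusion.** The point holds as a minor one. The sentence in SAP 5.4.1 uses an undefined term and the wrong unit. Its two possible readings can give opposite conclusions under Clopper-Pearson or Wilson. The supplied text plans no analysis to show what unknown primary outcomes could change, although one to three of them can decide the result under Clopper-Pearson. The worked examples show what is possible, not what is likely: they depend on the interval method, which SAP 6.1.1 leaves open, and on a missing rate the documents do not give. The fall in power from 85% to 78% is an illustration at an assumed 5% missingness with independent insertions, and there is no loss at 1%. It should not be read as an expected loss of power.

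**What to change.** Before database lock:

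1. Replace the sentence in SAP 5.4.1 with: *All mITT insertions with a known outcome are analysed, whatever the status of the same patient's other insertions; insertions with unknown outcome are listed with the reason.* Apply the same per-insertion rule to the lateral and angular deviations.
2. Add to SAP 6.1.1 one pre-specified sensitivity analysis against the same 0.88. It counts as failures both insertions with unknown outcome and planned insertions of mITT patients (assistance confirmed) for which no insertion is recorded.
3. State that the sponsor-consultation sentence in 5.4.1 does not apply to the primary endpoint, or that any such decision is made and documented without knowledge of the primary result. Otherwise it could override the new rule.
4. Correct both references in SAP 5.1: 5.5.2 to 5.4.1, and 5.5 to 5.4.

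The cost is SAP wording and one table. That table may look clearly less favourable. At a true 0.97 with 68 insertions, the Clopper-Pearson pass rate is P(Bin(68, 1 − 0.97(1 − m)) ≤ 3), which is 0.565 at m = 2% and about 0.21 at m = 5% random missingness. It should therefore stay a sensitivity analysis. The per-insertion rule keeps more data but is still complete-case, and does not by itself remove failure-linked bias.
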